The PIs are experienced in all aspects of the design, conduct and oversight of randomized controlled trials and prospective studies at multiple clinical sites and is an expert in the fields of medical decision-making, decision-assisting tool creation and evaluation. The Contact PI will take a lead role in all aspects of the proposed project, working with the Pi and site PI and staff members to ensure timely and accurate completion of the project. The Contact PI will direct day-to-day activities and provide overall governance and scientific leadership to the study.

Site Principal Investigator (site PI)

The site PI will meet as needed to contribute to the overall study design and ensure each site is executing the study as prescribed. The Site PI is responsible for hiring and training site staff and will provide clinical and research expertise in the design and implementation of study instruments and protocols. The Site PI will monitor study enrollment and troubleshoot any recruitment issues as needed. They will also assist with chart review for participant delivery outcomes as needed.

Research Coordinators/Managers

The Research Managers and Coordinators (RCs) are the primary administrative points of contact for the study. They will prepare and submit all materials for IRB approval including the initial application, renewals, and all modifications. They will pilot and fine-tune study instruments; screen, consent, and interview participants; abstract medical data from charts; and distribute participant remuneration. They will be responsible for following the guidelines for study operations outlined in this protocol and will email the Contact PI in the event of any protocol violations (e.g., erroneous inclusion of subjects in the study, breach of confidentiality). They will participate in conference calls as needed to go over recruitment and data collection activities and targets.

1.0 Study Summary

Study Title	Should I have an Elective Induction? The SELECTION Study
Study Design	Single arm pilot study of feasibility and acceptability of a decision support tool (DST) for elective induction of labor (IOL).
Primary Objective/Purpose	The goal of the proposed study is to perform a pilot test of a patient-centered DST to help women and providers work together in making informed, shared decisions regarding whether or not to opt for elective IOL at 39 weeks gestation
Secondary Objective(s)/Purposes	This study will provide the information needed to plan a randomized trial of the DST for support of the equitable offer of induction of labor.
Research Intervention(s)	Exposure to the decision support tool
ClinicalTrials.gov NCT #	NCT05838313
Study Population	Nulliparous people with singleton, vertex pregnancies at 36-38 weeks who are planning vaginal delivery and do not have a medical indication for induction of labor
Sample Size	60
Study Duration for individual subjects	Approximately 2 months
Study Specific Abbreviations/ Definitions	DST: decision support tool IOL: induction of labor CD: cesarean delivery

2.0 Background and Objective

The ARRIVE trial, a large multicenter study published in 2018, compared expectant management to induction of labor at 39 weeks absent medical indication and found that induction was associated with a decrease in CDs, preeclampsia/gestational hypertension, as well as in the need for neonatal respiratory support, without a statistically significant difference in adverse perinatal outcomes. Subsequently, both the American College of Obstetricians and Gynecologists (ACOG) and the Society for Maternal-Fetal Medicine (SMFM) issued statements that it was reasonable to offer elective induction of labor to low risk, nulliparous pregnant people (the population studied in the trial and the population who will be eligible for the current study). A study based on birth certificate data published in 2022 showed that the offer of elective induction of labor has been integrated into clinical practice. However, how, when, and to whom this option is offered is unclear. While the improvement in maternal and neonatal outcomes observed in this trial are compelling, little is known about how patients and providers view the routine offer of elective IOL at 39 weeks, which is a significant change in practice. Ultimately, the goal of this study is to support the equitable offer of elective induction of labor to all eligible people, and to support pregnant people in making an informed choice that is concordant with their values.

Cesarean delivery (CD) is the most common inpatient surgery in the US, accounting for nearly one third of births annually. Reducing the CD rate has been targeted as an important public health goal; however, achieving this goal has proven challenging. In parallel, delivery at 39 weeks has been suggested as optimal for the neonate, but controversy about the relationship between induction of labor (IOL) and CD has limited enthusiasm for utilizing IOL as a means of achieving delivery at this gestational age. Finally, the appropriateness of the intervening in pregnancy without a clear medical indication is highly controversial. Given the current professional American College of Obstetricians and Gynecologists (ACOG) guidance that: “Based on the findings demonstrated in this trial (ARRIVE), it is reasonable for obstetricians and health-care facilities to offer elective induction of labor to low-risk nulliparous women at 39 weeks gestation.”, potential complexity of discussions about elective IOL at 39 weeks and the significant population of women who likely will be presented with this option, a decision support tool (DST) may help to improve the efficiency of shared decision making and ensure incorporation of informed patient preferences around this offer. The goal of the proposed study to conduct a pilot study of the impact, feasibility, and acceptability of a prototype decision support tool for elective induction of labor.

3.0 Study Design and Hypotheses

This is a single arm prospective clinical trial to collect pilot data for planning a future study of the impact of the Elective IOL DST, the intervention of interest, on induction rates, cesarean delivery rates, decision quality and resource use. The primary goal of this pilot is to determine the acceptability of the Elective IOL DST, to assess the feasibility of recruiting and retaining study participants in anticipation of future effectiveness and implementation studies, and to finalize outcome and other measures. The descriptive analyses planned include cross-sectional analyses, which will consist of profiles of the sample, including examination of means and proportions, measures of variability, and confidence intervals around these statistics. We also will investigate relationships within and between measurement domains (e.g.

demographics, outcomes), although these will only be exploratory in nature. In addition, we will describe the trajectories of participant responses across time.

As a pilot study, there are no hypotheses to be tested; therefore formal sample size calculations are not appropriate.

4.0 Study Intervention

The Elective Induction of labor decision support tool is viewed on a tablet, phone, or computer. It includes information regarding induction of labor, the potential benefits and risks of induction and expectant management, as well as values clarification questions to help people to think through what matters most to people as they consider their decision. In this single arm pilot trial, all participants will view the decision support tool.

The current project is the third part of a three-part study funded by the NIH. The overall goal of the project is to develop a patient-centered decision support tool to help women and providers work together in making informed, shared, values concordant decisions regarding whether or not to opt for elective IOL at 39 weeks gestation.

We have continued to improve upon the process that our group has used to develop other patient-centered prenatal care-related DSTs, which have been tested in NIH-funded, multicenter, randomized clinical trials among English- or Spanish-speaking pregnant women (R01HD078748, R01HD04968). The design process we have used to develop our DSTs follows the standards put forward by the International Patient Decision Aids Standards (IPDAS) Collaboration, using a systematic development process based on the IPDAS quality checklist. We utilize a patient-centered approach, which always begins by examining the needs, desires, and behaviors of the target population. We rely on published, validated literature for the information included in the decision support tools and utilize an iterative process to obtain input from patients and health care providers regarding their views on informational and decision-support needs. Using this patient-centered design approach, our designers work with researchers, providers, and patients to leverage the expertise of all parties in ways that exceed standard expectations for the engagement of these parties in research. This approach allows us to better connect with the people who are the center of our research, and enables quick and effective transformation of data into actionable ideas/tools.

In developing this tool, we began by conducting formative research to gain an understanding of how women and providers view the potential offer of elective induction of labor at 39 weeks gestation. We interviewed pregnant and postpartum women, to determine what they know and feel about elective IOL at 39 weeks and how they would view being presented with a choice between this intervention versus expectant management. We also interviewed providers (obstetricians, midwives, prenatal nurses and labor and delivery nurses) to obtain their thoughts on elective IOL at 39 weeks, how they view the latest data on its role, and how comfortable they would feel offering this option to their patients. We transcribed and coded these interviews and continued interviews until thematic saturation was reached. Based on our findings and the published literature and professional guidance regarding elective induction of labor, we created the prototype patient-centered DST. The DST begins with the statement “Your health care providers can tell you a lot about these two approaches and the advantages of each, but YOU are the expert about what is important to you” and aims to

present balanced information to support the user in making an informed, values concordant choice between the two options. It presents information on elective IOL at 39 weeks versus expectant management, including information regarding the processes and potential outcomes of each approach to delivery, and incorporating values clarification exercises as well as a summary statement that women can use in discussing this option with their providers. We then pretested the tool in pregnant and postpartum women and reviewed it with providers to obtain their feedback on the content and presentation, iteratively using that process to improve the prototype.

4.0 Study Population

Inclusion and Exclusion Criteria

This study will include 60 pregnant people at two sites. Eligibility criteria will include nulliparity, singleton pregnancy, no contraindication to vaginal delivery, no medical indication for IOL, age 18 years or older and an ability to speak English (as study materials are only available in English at this time). Exclusion criteria will include people not planning a vaginal delivery, people who have had a baby in the past, people with a medical indication for induction of labor at the time of enrollment, people younger than 18

Participant Withdrawal

People who experience a pregnancy loss (stillbirth) will not be contacted for any additional study visits. This is expected to be an extremely rare event in this low risk population. People may also request to be withdrawn from the study if they no longer want to participate.

5.0 Recruitment

Each site will utilize the same recruitment methods that we have used successfully in prior studies of pregnant people. We will ensure that all necessary human subjects' reviews and approvals are obtained prior to implementation at any recruitment site.

Potentially eligible participants will be identified by reviewing outpatient charts to identify pregnant people who meet the eligibility criteria. At all sites, both academic and "private" practices are associated with an academic health system, and as such, with IRB approval, study staff is able to remain HIPAA-compliant when they pre-screen patients.

At USF, eligible people will receive a letter describing the study, signed by a leadership representative of their OB practice (as many patients do not have a single provider they see for prenatal care, but rather see a team of providers). A stamped return "opt in/out" card will be included, which the recipients can return to indicate that they are either interested or not interested in hearing from the study staff. The site-specific interviewer's telephone number also will be included for each recipient's use if they prefer to use this method of communication. Respondents who check "opt in" will be called/contacted by the method they state they prefer. Those who opt out will not be contacted. A study staff member will come to a subsequent visit at which time the clinical staff will ask the participant if they would be willing to discuss the study and assess their eligibility and interest in participating. The "opt out" mechanism has been shown to yield a more diverse group of participants than the "opt in" approach, and, in our many studies of diverse populations, has been highly effective in recruiting participants for

studies that require conducting face-to-face interviews with pregnant people at specific gestational ages.

At OSU, eligible people will receive a brochure detailing the study. Those who are eligible and interested will be contacted to set up an enrollment interview.

Participants will be identified starting at 32-34 weeks with the goal of scheduling the initial study visit between 36+0 and 38+0 weeks gestation to allow time to view and consider the information in the decision tool prior to making a decision regarding whether to proceed with an elective induction at 39+0 to 39+6 weeks gestation.

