5.0 Study Procedures

The procedures and/or interventions conducted as part of this research are low risk, educational interventions. Elective induction, or induction of labor absent medical indication is an evidence-based aspect of routine pregnancy care that has been endorsed by the OBGYN professional society guidelines as being reasonable to offer since 2018. In clinical practice, the way that this option is offered is currently highly variable and driven by the provider rather than by the patient's preferences and goals. The intervention in this study will be the viewing of standardized information about elective induction of labor prior to making their decision about this option with their provider. Questionnaires will be utilized to understand the impact of the educational intervention on decision quality and the feasibility and acceptability of the intervention.

We will prospectively enroll 60 nulliparous people (approximately 30 at USF and 30 at the Ohio State University) planning vaginal delivery with singleton, vertex pregnancies at 36-38 weeks who do not have a medical indication for IOL to view the DST. During their enrollment face-to-face interview, they will review the DST and complete pre- and post-DST viewing questionnaires. We will conduct telephone interviews a few days later but before 39+0 weeks, and again 2-4 weeks postpartum. During these interviews, we will collect information on the acceptability of the tool and decision quality. We also will include an open-ended question in the postpartum interview to obtain feedback on topics and information the participants wish had been included in the DST.

At the time of enrollment, written informed consent will be obtained by the study research coordinator. The consent form will include information about the purpose of the study, the nature of the subject's participation, the possible risks and discomforts associated with participation, the potential benefits of participation, a statement of the voluntary nature of participation, and a description of the mechanisms used to ensure confidentiality. A study eligibility checklist will be completed prior to any study procedures. Parental consent will be obtained to review the medical records of the infants. Assent is not appropriate given the clinical scenario (review of infant medical records).

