7.0 Data Management and Confidentiality

We will take extensive precautions to maintain participant confidentiality throughout the study. First, lists of individuals who will be participating will be kept in a locked drawer and in password protected computer files in the office of the study coordinator at each site. Used consent forms will also be locked in a filing cabinet in the office of the study coordinator. Confidentiality of all study-related records will be maintained in accordance with State and Federal laws.

Three databases will be maintained for the study: 1 and 2) Site specific “participant tracking” databases will contain all identifying information that will permit locating participants for their interviews, ensuring that interviews are completed on time, and performing chart reviews. It will include demographic information for all patients who do not meet the eligibility criteria or who decline participation, along with their reasons for refusal (to permit comparisons between those who do and do not enter the study). 2) A single “study data” database will contain all project-related data used for the analyses. Participants will be identified only by a code number in the study database.

Obstetric clinic schedules will be reviewed to screen for eligibility, so that only subjects meeting eligibility criteria will be approached. We will keep the minimum information necessary (Name, MR#, appointment date and time) in the recruitment database so that we know who has an appointment and can make sure recruitment materials are available when they are in clinic. People who decline will be marked as declining so that they are not approached again. Records reviewed will only be from people who are actively receiving prenatal care and scheduled for appointments within the 4 weeks prior to the timeline for the study. Only study staff will have access to the RedCap database. Because we can only identify eligible patients based on medical record review, it is not practical to obtain consent prior to the approach. Identifiers will be removed within 6 months and only information needed to inform the CONSORT diagram will be maintained.

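### Do the differing recruitment descriptions for the two sites, and the lack of named recruitment and retention rates in the analysis plan, call for a change?

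*Combined protocol and SAP*

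**What the plan says.** The Recruitment section opens: "Each site will utilize the same recruitment methods that we have used successfully in prior studies of pregnant people". For USF it describes a letter, a return card for opting in or out, direct contact with those who opt in, and a later approach in clinic: "A study staff member will come to a subsequent visit at which time the clinical staff will ask the participant". It says the opt-out "mechanism has been shown to yield a more diverse group of participants than the" opt-in approach and, "in our many studies of diverse populations, has been highly effective in recruiting participants". The OSU text is two sentences, covering a brochure and then contact to arrange enrollment: "At OSU, eligible people will receive a brochure detailing the study. Those who are eligible and interested will be contacted".

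Study Procedures gives the split as "approximately 30 at USF and 30 at the Ohio State University".

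Section 7.0 sets up site-specific tracking databases. They hold demographics and refusal reasons for people who are ineligible or decline, "to permit comparisons between those who do and do not enter the study". The same section describes an approach in clinic without naming a site, marks decliners, and refers to a CONSORT diagram. Section 9.0 requires reports of the numbers enrolled and completing.

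Section 10.0 includes the feasibility of recruitment and retention in the primary goal. It plans means, proportions, measures of variability, confidence intervals, exploratory relationships and trajectories over time, and states that no hypothesis is tested.

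**The concern.** Two things look wrong.

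First, the protocol says one recruitment route gives a more diverse sample, yet half the sample appears to come by another. The opening sentence can be read as promising the same methods at both sites. The secondary purpose is to "plan a randomized trial of the DST for support of the equitable offer of induction of labor". If OSU contacts only people who have already shown interest, its sample might be less diverse, and a pooled description would mix two recruitment processes.

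Second, section 10.0 does not turn the feasibility goal into named quantities. A recruitment rate means little until its base is known: people eligible on chart review, sent material, or contacted. The comparison for which section 7.0 collects data is not mentioned again in section 10.0. A team planning the later trial could be given one percentage with no clear base and no view of who stayed out.

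**Working it through.** **1. Site shares.** 30 + 30 = 60, so OSU supplies 30/60 = 50%. The figure of 60 comes from no formula, so there is no power or precision target to reproduce.

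**2. Is there a contradiction in the Recruitment section?** The phrase about the same methods is completed by a reference to prior studies, so its natural comparator is those studies and not the other site. The section says opt-out worked well in many studies. It does not say that every prior study used only opt-out, or that none used a brochure. OSU is never labelled opt-in, and how interest is established there is not stated. Section 7.0 has staff making sure recruitment materials are on hand when patients attend, and approaching only eligible people, at no named site. A brochure given in clinic fits that description. USF is not purely opt-out either, since its card allows both answers. The OSU text is shorter, but a conflict is not shown.

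**3. What would a real site difference do?** With a 30:30 split, a gap of D points in a participant characteristic places the pooled figure D/2 from each site: 5, 10 or 15 points for D = 10, 20 or 30. D is assumed, because the documents give no value. The trial has no comparison between arms that such a gap could bias.

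**4. Does the missing denominator lose information?** With 60 enrolled, the rate is 60/N. For assumed N of 80, 120, 200 and 300 it is 75%, 50%, 30% and 20%. The choice of base therefore matters for one quoted percentage. A CONSORT diagram reports the counts behind such a percentage, so a reader can see the base used. Retention is completed/enrolled, and section 9.0 requires both counts.

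**5. Would a by-site table add much?** Wilson 95% intervals, for assumed proportions of 50% and 90%:

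| Proportion | n = 60 | Half-width (points) | n = 30 | Half-width (points) |
|---|---|---|---|---|
| 50% | 37.7–62.3% | 12.3 | 33.2–66.8% | 16.8 |
| 90% | 79.9–95.3% | 7.7 | 74.4–96.5% | 11.1 |

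For a difference between two sites of 30, the Newcombe 95% interval is ±23.8 points when both are at 50% and ±16.9 when both are at 90%. Only very large site differences would be distinguishable. Site and recruitment method could not be separated in any case.

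**6. Are the data for a fuller table planned?** Only in part. Section 7.0 lists demographics for ineligible people and decliners, not for those who never respond. A table describing everyone who did not enter would need data beyond what that section lists, on people who have not consented.

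**The case for a change.** The strongest case for a change is that recruitment and retention are part of the primary goal, so their measures deserve the same definition as any primary quantity. General wording about proportions with confidence intervals describes people already enrolled, and a recruitment rate also needs the people who were not. Timing adds to this. Section 7.0 removes identifiers within 6 months and then keeps only what the CONSORT diagram needs. It also limits the recruitment database to name, record number and appointment details. It is fair to ask which non-entrant fields would survive for the comparison.

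Part of this stands. Section 10.0 does omit the rates and the comparison, and section 7.0 is loosely worded on what is kept about non-entrants. But section 7.0 states the purpose of the demographic data outright, so the study team has reason to tabulate them before they are removed. The flow counts are the part expressly retained. Repeating in section 10.0 a purpose already given in section 7.0 would be tidier, but it would not change what a competent analyst produces.

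**Conclusion.** The concern points to missing detail, not to a rule or figure that gives a wrong result. Followed as written, the plan yields a sound description: enrolled and completed totals, a participant flow, refusal reasons, and a comparison with ineligible people and decliners. Analysts would be expected to state the base of any rate they report. The OSU recruitment text is brief, and the documents do not show that it describes a less inclusive route.

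The effect is confined to how conveniently the pilot can be read. No test or estimate between arms is involved. By-site tabulation is optional, with half-widths up to 16.8 points per site and about 17 to 24 points for a site difference at the two proportions examined.

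This rests on three assumptions: the site split is close to 30:30, the CONSORT counts are kept as section 7.0 says, and the non-entrant comparison is made from the groups that section 7.0 names. No change to the plan follows.
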